# 6.2. Local Tolerability

The primary ISR endpoint will be assessed at least twice on Day 0: immediately after [ie, as soon as possible but no later than 10 minutes upon removing the needle] and again 1 hour after each of the four injections; on Days 1, 3, 7 and 14; at Months 3 and 6, and at additional visits, if indicated. The frequency with which subjects experience any ISR as well as those experiencing each category of ISR documented on the case report form (i.e., redness, swelling, itching, bleeding, bruising, skin discoloration, atrophy/dimple) will be summarized by treatment group, as well as ISRs that meet the per-protocol definition of an AE. Data listings will include time to onset, duration, and resolution of the ISR.

For an ISR type, if there are sufficient numbers of ISRs to warrant the use of asymptotic methods, pair-wise treatment odds ratios (for all 6 possible comparisons among 4 treatment groups) will be assessed using logistic regression models with generalized estimating equations and robust variance estimation to account for the correlated nature of the data. The primary model will only include effects of treatment group. An exchangeable working correlation structure will be used to estimate covariance parameters. Parameter estimates, standard errors, 95% CIs, Z scores, and p-values for parameter group comparisons will also be produced. Exploratory analyses may be performed to assess effect of injection order, age and race if the population is deemed sufficiently heterogeneous with respect to these factors (based on opinion of lead statistician, in blind review of data). For less frequent ISR types (i.e., those determined not to be amenable to asymptotic method analysis), differences between groups will be assessed using exact McNemar's tests (separately for each of the 6 possible treatment comparisons). A final determination of whether the asymptotic method is appropriate will be made by the lead statistician based on observed correlation structures and event rates, blinded to treatment group prior to database lock and unblinding. In particular, if the expected coverage error of 95% confidence intervals is predicted to be below 90% (as determined in simulation studies), then the exact method will be used.

Local Tolerability Study - Contraception Statistical Analysis Plan Version 2.0 TV46046-WH-10147 /1191167 Although excluded from the primary analysis of ISRs, data from partial injections will be summarized in listings and described when summarizing the overall safety results.

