1.2.2. Clinical Studies

Based on the interim analysis of safety data from the TV-46046-WH-10075 study on 28 August 2017, eleven out of 12 study subjects reported at least one sign or symptom consistent with an ISR that included but was not limited to pain, redness, tenderness, swelling, bruising, itching and sense of pressure during injection. Nine of the reported ISRs met the per protocol definition of an adverse event. All nine adverse events were mild in severity, lasted on average 4 to 5 days and resolved without sequelae. Two women had hypopigmentation of skin at the site of injection (ie, injection site discoloration) that appeared between 3 and 4 months after the injection, respectively. Both areas of hypopigmentation were approximately 2 cm in diameter and both were still present 6 months after the injection. More detailed information on the results of the Phase 1 study may be found in the current investigational brochure (IB).

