## 3. ANALYSIS SETS

There will be a single analysis set defined for this study: the Treated Analysis Set, which will include all subjects who receive at least 1 of the 4 study injections. All analyses will be performed according to treatment group received, even if the result of a randomization or

Local Tolerability Study - Contraception Statistical Analysis Plan Version 2.0 TV46046-WH-10147 /1191167 allocation error. During the study, several subjects reported receiving partial injections due to syringe blockage. In a blinded review of the data and in consultation with the SRC, it was decided that partial injections will be excluded from the primary safety analysis and subjects who experienced any partial injection will be excluded entirely from the secondary pain score analysis. Detailed information regarding the partial injections and the impact on study conduct as well as analyses are documented in Section 8.1.

Any other decision to exclude subjects or data points from this analysis set (e.g. due to important protocol deviations) will be made in blinded data review and documented in the CSR.

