# 8. CHANGES TO ANALYSES SPECIFIED IN PROTOCOL V1.0

# 8.1. Changes from V1.0 of SAP, prior to interim analysis

In consultation with the SRC and in a completely blind data review, the decision was made on April 26th 2019 to enroll 3 additional subjects because 3 of the planned total of 24 received only partial injections of one of the drugs. Based on this consultation, the decision was made to exclude partial injections from the primary safety analysis and to entirely exclude subjects who experienced a partial injection from the secondary pain score analysis. All subjects, regardless of any partial injections, remain included in the assessment of overall safety per section 1.2.2.2. Demographic data will be summarized for both the Treated Analysis Set and the subset of subjects who received no partial injections of drug.

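### SAP 6.2 mis-states its trigger for exact McNemar, and has no rule for a pair with a zero-event treatment once GEE has been chosen

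*SAP*

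**What the plan says.** SAP 6.2 compares treatments pairwise for each ISR type, with two possible methods.

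- **GEE.** Logistic GEE with treatment as the only effect, exchangeable working correlation and robust variance is used "if there are sufficient numbers of ISRs to warrant the use of asymptotic methods". It yields odds ratios, intervals and p-values for all six pairs.
- **Exact McNemar.** This is used for all six pairs of an ISR type judged unsuitable for asymptotics.

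The choice "will be made by the lead statistician based on observed correlation structures and event rates, blinded to treatment group prior to database lock and unblinding". The one numerical criterion sends a type to the exact method "if the expected coverage error of 95% confidence intervals is predicted to be below 90% (as determined in simulation studies".

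Protocol 8.6.1 has the same blinded choice but no threshold. Neither document says what happens if GEE has been chosen and one treatment then has no events, or events in every woman.

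The analysed data will be unbalanced. SAP 3 states that "partial injections will be excluded from the primary safety analysis", and SAP 8.1 records that "3 of the planned total of 24 received only partial injections of one of the drugs" and that three women were added.

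**The concern.** There are two separate defects.

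1. **The trigger names the wrong quantity.** Coverage error is either the departure from 95% or, at most, the non-coverage, nominally 5%. Both are practically always below 90%. Taken at its word, the sentence selects exact McNemar every time and contradicts the GEE plan in the same paragraph.

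2. **The choice is made for the ISR type, but the failure occurs in a pair.** An ISR can be common on TV-46046 and absent on another treatment. Once such a type is assigned to GEE, every pair that includes the zero-event treatment has an infinite odds ratio. The documents provide no pair-level fallback.

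At stake is the primary comparison of tolerability. It is tested at a two-sided 0.05 level without multiplicity adjustment (Protocol 8), and two equally tolerated treatments could be reported as different. SAP 2.6.2 classes supportive analyses not identified in the SAP as exploratory, so an exact test substituted after the zero is seen risks that label.

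**Working it through.** **Inputs.** N = 24. Redness in Protocol Table 3 is 9/12 (75.0%) on TV-46046 and 1/18 on Depo-subQ 104; hypopigmentation on Depo-subQ 104 is 0/18. Rates for diluted TV-46046 and placebo, and the within-woman correlation, are not in the documents and are assumed below.

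**The plan's own figure.** The chance of at least one event at a true rate of 10% is 1 − 0.9^24 = 0.920. This agrees with the stated figure of more than 90%. The same formula gives the chance of a zero.

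**How likely is a zero?** P(0 of n) = (1 − p)^n. For two treatments with the same rate and independent responses, P(exactly one has zero) = 2 × P(0) × [1 − P(0)].

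| True rate | P(0/24) | Exactly one of two has zero |
|---|---|---|
| 1/18 | (17/18)^24 = 0.254 | 2 × 0.254 × 0.746 = 0.38 |
| 10% | 0.9^24 = 0.080 | 2 × 0.080 × 0.920 = 0.15 |
| 1/6 | (5/6)^24 = 0.013 | 2 × 0.013 × 0.987 = 0.025 |

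With 27 women and no exclusion on a treatment, P(0/27) at 1/18 is 0.214. Events in all women are less likely: P(24/24) is 0.1% at 75% and 12% at 11/12. The latter rate is where "eleven out of 12 study subjects reported at least one sign or symptom consistent with an ISR", and it includes pain, which the primary endpoint excludes.

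**Can a blinded choice miss it?** Counts of 18/12/6/0 and 9/9/9/9 out of 24 both pool to 36/96 = 37.5%. GEE fits the second normally; the first has no finite odds ratio in three of the six pairs.

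**Does the corrected trigger catch it?** That depends on the simulation set-up, which the SAP does not specify.

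- Equal rates of about 33% in both treatments: coverage is 94–95%, so GEE is kept.
- 75% against 1/18, independent responses: 74.4% of fits are estimable and 95.6% of those cover. Dropping the other fits gives about 96% (GEE kept). Counting them as misses gives 0.744 × 0.956 = 0.71 (exact method chosen).
- At equal rates the counting convention changes the choice only up to about 12%. At 10%, coverage is about 99% with such fits dropped and 84–87% with them counted.

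**What GEE returns.** For 18/12/2/0 of 24 (pooled 32/96 = 33%), statsmodels GEE with exchangeable correlation and robust variance reports convergence. For 2/24 against 0/24:

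- Reference is any treatment with events: log odds ratio about 23–29, standard error 0.77, p far below 0.001.
- Reference is the zero-event treatment: the standard error is huge or undefined, so there is no usable p-value.
- Exact McNemar, two discordant women in one direction: p = 2 × 0.5^2 = 0.50.

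**False significance for an equal pair.** In simulated trials with 24 complete women, two treatments at 1/18 and the others at an assumed 75% and 50%, GEE converged with p < 0.05 for the equal pair in about 41% of trials when a common-event treatment was the reference. The figure was 19–22% when one of the two rare treatments was. The table explains this, within simulation error. With a common-event reference, nearly every trial with exactly one zero (38%) gives a false result. With a rare-event reference, the zero falls on the reference in half of those trials, leaving 0.38 / 2 = 0.19. At 1/6 the rate is 3–5%, so there is no excess.

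**The case against.** The case on the other side is substantial.

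- **The wording slip is editorial.** SAP 6.2 spends most of a paragraph on GEE output, so no statistician would take its last sentence as banning GEE. That stands: the intended meaning is clear. It is still the only numerical criterion for choosing the primary test, and it should say what it means.
- **The blinded review might see the zero.** A reader might infer that any ISR type with a zero-event treatment must pass to GEE. The documents do not support that. The phrase "based on observed correlation structures and event rates, blinded to treatment group prior to database lock and unblinding" would also fit rates by masked treatment code, and the simulations could include zero-event treatments. The SAP specifies neither, and neither would supply a pair-level rule after GEE is chosen.
- **The false p-value depends on coding and software.** This stands. The size moves with the reference treatment, and SAP 7 specifies SAS, which was not run and may flag non-convergence. Under every coding tried, though, the zero-event pair had no valid GEE result.
- **The harm is limited.** Counts by treatment are tabulated, so 2/24 beside 0/24 with an enormous odds ratio would look odd. The risk falls mainly on rare ISR types, and this is a small Phase 1 study without a success rule. All true, and it argues against calling the problem grave.
- **The SAP already names an alternative test.** Correct: exact McNemar is there. Only the rule that applies it to a single pair is missing.

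**Conclusion.** The point holds in two parts. The trigger is wrong as written and should refer to coverage probability. Separately, SAP 6.2 lacks a rule for pairs in which a treatment has zero events, or events in all women, after an ISR type has been assigned to GEE.

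A zero is foreseeable: 25% for a treatment at 1/18 with 24 women, and 38% for exactly one zero between two such treatments under independence. The rate of 1/18 rests on a single event.

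A reader might take 38% or 41% as this trial's false-positive rate. The documents do not support that. The simulated range is about 19% to 41%. It is conditional on the reference treatment, on statsmodels, on two treatments both near 1/18 and on assumed rates for the other two, and the excess is gone near 1/6. What does not depend on those choices is that a pair with a zero-event treatment has no finite odds ratio, and the plan does not say how it is then tested. This should be fixed before database lock.

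**What to change.** Make two changes to SAP 6.2.

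1. In the last sentence of the method-choice paragraph, replace *coverage error* with *coverage probability*, and state that simulated fits without a finite odds ratio count as non-coverage.
2. Add: *Any pair in which either treatment has zero events, or events in all women, among the injections analysed will be tested by exact McNemar as a prespecified analysis. That treatment will be left out of the GEE fit for the remaining pairs. The analysis program applies this rule, so no unblinding is needed.*

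The cost is two wording changes and one program rule. No odds ratio is reported for the affected pairs, and exact McNemar is conservative there: 5/24 against 0/24 gives p = 2 × 0.5^5 = 0.06, and significance needs 6/24 against 0/24, p = 2 × 0.5^6 = 0.03. In the simulations at 1/18, the pair rule reduced false significance for the equal pair to 0–0.3%.

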# 6.3. Injection Site Pain

NRS pain scores for assessments on the day of injection (Day 0) will be summarized by treatment group in frequency tables, separately for pain measured immediately after injection and at 1 hour after injection. If an appropriate distribution of pain scores can be identified in blinded review (e.g., negative binomial or Poisson), then generalized linear models with exchangeable working correlation structure to account for correlated data will be used to compare treatment groups. The analysis model will only include effects of treatment, but exploratory analyses will be performed to assess effects of injection order, age, and race. If the dispersion of NRS scores is not amenable to parametric regression methods, then rank-order, permutation tests will be used to compare treatment groups (excluding any subjects who did not receive both injections being compared).

Approximately 1 hour after completing their sequence of the four treatments, each subject will also be asked to rank the injections according to overall pain from least [1] to most [4] painful. The ranking of treatment group pain will be summarized in bar charts and frequency tables, restricted to subjects who received all four injections. Differences in ranking of most painful injection will be assessed using an exact multinomial test for homogeneity across groups. If a subject cannot rank all of her injections from least to most painful, or cannot uniquely identify which injection was most painful, then her responses will be appropriately weighted across groups (e.g., if a subject ranks all 4 treatments as equally most painful, then that subject will contribute a score of 0.25 to each group when assessing distribution of most painful injection).

The proportion of subjects with unsolicited reports of injection site pain at one or more follow-up visits after Day 0 will be tabulated and compared between treatment groups using exact, pairwise McNemar tests.

Listings of pain score data will include subjects who received partial injections.

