8. STATISTICS

This section describes statistical analyses of primary and secondary objectives as foreseen at the time the protocol was written. Further details will be described in a separate statistical analysis plan which will be approved prior to unblinding of study statisticians. Any additional analyses or changes to planned analyses will be fully disclosed in the clinical study report. All statistical analyses will be performed using SAS[®] software Version 9.4 or later. All tests and comparisons between treatment groups will be conducted at the two-sided 0.05 significance level, with no adjustment for multiple comparisons.

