#### 2.5. Sample Size and Power Considerations

The study size of 24 subjects (N=24) will provide at least 80% power to detect differences in ISR rates of the magnitude (>40%) observed in recent non-comparative studies of TV-46046 and Depo-subQ 104. Although not designed to obtain precise estimates of less frequent ISR rates (eg, injection site discoloration [hypopigmentation]), there is a high (>90%) probability of detecting one or more specific ISR types if the true rate of such events is at least 10%. No randomized subjects will be replaced. However, if more than two subjects fail to receive all four injections or discontinue before Month 6, then additional subjects may be enrolled to help ensure that there are at least 22 who complete the treatment sequence and are evaluable for at least 6 months. The

Local Tolerability Study - Contraception Statistical Analysis Plan Version 2.0 TV46046-WH-10147 /1191167 additional subjects will be assigned new randomization numbers, and will not re-use the randomization numbers from subjects who did not received all 4 injections.

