# 4. GENERAL ISSUES FOR DATA ANALYSIS

#### 4.1. General

Descriptive statistics for continuous variables will include the number of observed values, the mean, standard deviation (SD), median, minimum, and maximum values. For categorical variables, the number and percentage of subjects with a specific level of the variable will be presented.

All reported p-values will be assessed for statistical significance at the two-sided 0.05 level, and all confidence intervals (CIs) will be computed at the two-sided 95% coverage level.

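### The GEE comparisons rest on about 24 to 27 women with no small-sample correction: ISR tests exceed the stated 5% at mid-range event rates, and the pain model leaves its variance estimator and reference distribution unstated.

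*SAP*

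**What the plan says.** Error rate. SAP 4.1 states that "All reported p-values will be assessed for statistical significance at the two-sided 0.05 level" and sets confidence intervals at 95%. Protocol section 8 adds: "All tests and comparisons between treatment groups will be conducted at the two-sided 0.05 significance level, with no adjustment for multiple comparisons".

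ISRs, the primary endpoint (SAP 6.2). All six pairwise odds ratios come from a treatment-only logistic GEE with exchangeable working correlation and robust variance. "Parameter estimates, standard errors, 95% CIs, Z scores, and p-values for parameter group comparisons will also be produced". The asymptotic method is used only if there are enough events; otherwise exact McNemar tests apply. The lead statistician decides while blinded. One trigger is named: use the exact method if simulation predicts that the coverage of 95% intervals is under 90%.

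Day 0 pain, a secondary endpoint (SAP 6.3). If blinded review identifies a suitable distribution, with negative binomial and Poisson given as examples, "generalized linear models with exchangeable working correlation structure to account for correlated data will be used to compare treatment groups". Otherwise rank-order permutation tests are used. The section mentions no robust variance, Z score, degrees of freedom or coverage check.

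Number of women. SAP 8.1 records the decision to "enroll 3 additional subjects because 3 of the planned total of 24 received only partial injections of one of the drugs". SAP 3 excludes partial injections from the ISR analysis, while "subjects who experienced any partial injection will be excluded entirely from the secondary pain score analysis".

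**The concern.** A model with a working correlation structure is a GEE, and its robust variance is justified by a large number of clusters. Here a cluster is a woman, and there are about two dozen. The uncorrected robust variance uses a divisor that is too small for the degrees of freedom, and a Z score is then compared with 1.96 where a t quantile would be larger. In the simple case of a mean difference both errors make intervals too narrow and tests too liberal.

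At stake is whether a reported p-value below 0.05, or a 95% interval, has the property that SAP 4.1 assigns to it. In SAP 6.2 the method is written down. In SAP 6.3 the choice that decides the answer is left open until analysis.

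**Working it through.** **Inputs.** Two-sided 0.05 (Protocol 8, SAP 4.1). Planned n = 24 (SAP 2.5). Up to 24 + 3 = 27 women for ISRs and 27 - 3 = 24 for pain (SAP 8.1 and 3); 21 for pain would apply only without the three added women. The documents give no within-woman correlations or pain-score distributions, so those below are assumptions. Complete data are assumed.

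**1. The plan's own figures.** SAP 2.5 claims "at least 80% power to detect differences in ISR rates of the magnitude (>40%) observed in recent non-comparative studies". The two-proportion formula with 24 per group is power = Φ{[Δ - 1.96√(2p̄(1-p̄)/n)] / √[(p1(1-p1) + p2(1-p2))/n]}. For 70% against 30% it gives Φ{(0.40 - 1.96 × 0.1443)/0.1323} = 0.81, and for 45% against 5% it gives 0.92. The chance of at least one event at a 10% rate is 1 - 0.9^24 = 0.920, against the stated figure of over 90%. Both claims reproduce on this basis and are not in question.

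**2. Form of the robust variance.** With treatment as the only effect and complete crossover data, the fitted means are the sample means. The robust variance of a pairwise contrast is then Σe_i²/n², where r is a residual and m a treatment mean:
- mean difference: e_i = r_i1 - r_i2
- log link: e_i = r_i1/m1 - r_i2/m2
- logit link: e_i = r_i1/[m1(1-m1)] - r_i2/[m2(1-m2)]

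On a simulated data set of 24 women by 4 treatments, GEE software and the log-link formula both gave a standard error of 0.17657.

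**3. Pain as a mean difference, if robust SE and Z are used.** Here Σe_i²/n² = s²(n-1)/n², so Z = t√(n/(n-1)). The test rejects when |t| with n-1 degrees of freedom exceeds 1.96√((n-1)/n). For n = 24 that cut-off is 1.96 × √(23/24) = 1.919, against a correct t value of 2.069.

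| n | True size | Interval width relative to t-based |
|---|---|---|
| 21 | 7.02% | 91.7% |
| 24 | 6.75% | 92.8% |
| 27 | 6.55% | 93.6% |

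**4. Pain with a log link.** Null simulations used Poisson, negative binomial and rounded normal scores on 0 to 10, with within-woman correlation about 0.15 to 0.57 and 40,000 runs each. At n = 24, robust SE with Z gave 6.4% to 8.1%, highest for skewed low scores. Model-based SE with Z gave 4.0% to 5.1%.

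**5. ISRs with robust SE and Z, as SAP 6.2 states.** All paired 2×2 tables were enumerated for n = 24, equal rates and within-woman correlation 0.3. Sizes are among tables where the odds ratio is estimable.

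| ISR rate | Robust SE, Z | n/(n-1) scaling, t on 23 df |
|---|---|---|
| 10% | 1.1% | 0.6% |
| 20% | 4.1% | 2.7% |
| 30% or 70% | 5.6% | 4.1% |
| 40% or 60% | 6.6% | 4.3% |
| 50% | 7.0% | 4.3% |
| 75% | 5.0% | 3.6% |

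With 27 women the peak is 6.9%. With zero correlation and 24 women it is 6.4% at 50% and 4.7% at 30% or 70%.

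**6. Do the safeguards catch it?** A size of 7% corresponds to coverage of about 93%, which is above the 90% trigger in SAP 6.2. In SAP 6.3 the permutation fallback depends on the dispersion of the scores, not on the number of women.

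**7. Effect of a correction.** Scaling the variance by n/(n-1) but keeping Z gives 2P(t on 23 df > 1.96) = 6.2% at n = 24, so the t reference is needed too. With both parts, size is 5.0% for a normal mean difference and 4.4% to 6.4% for the log-link scores over n = 21, 24 and 27. For ISRs at n = 24 it is at most 4.3%.

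**The case against.** A reader might infer that every pain and ISR comparison runs at 6.5% to 7%. The documents do not support that, for three reasons.

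- SAP 6.3 names neither robust variance nor Z scores. Those terms appear only in the ISR text, and nothing says that the ISR convention governs pain. With model-based errors the size is about 5%. The parametric model is also conditional on the blinded review, and the pain ranking and the follow-up pain comparisons already use exact tests.
- For ISRs the excess is confined to mid-range rates. The planning rates in Protocol Table 3 are 75.0% and 5.5% for redness and 16.7% and 0% for hypopigmentation, none of them near 50%. This stands, although the table gives no rates for the diluted product or the placebo.
- SAP 6.2 does plan for small samples. The blinded switch to McNemar tests considers event rates and correlation, and the 90% figure is introduced as a particular trigger, not necessarily the only one. That is fair, but it is the only numerical criterion given, and it would accept 93%.

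It can also be said that one or two points of excess size matter little in a Phase 1 study that tests six contrasts per outcome without multiplicity adjustment. That lowers the priority. It does not make the stated per-test level correct.

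**Conclusion.** The concern holds in a limited form. For ISRs, the written method (robust variance with Z scores and no correction) has true size of about 5.6% to 7.0% at event rates of 30% to 70% with 24 women. It is nominal at 75% and conservative at 20% or below. These figures rest on an assumed correlation of 0.3 and complete data. The stated coverage trigger would not remove the excess.

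For pain, the supportable finding is an omission: the variance estimator and reference distribution are unstated for about 24 clusters, and there is no coverage check. The 6.75% figure, and 6.4% to 8.1% for log-link scores, apply only if the ISR convention is carried over and the parametric model is chosen.

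Importance is minor to moderate: the effect is small, pain is secondary, and the study makes no claim to familywise control.

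**What to change.** State in SAP 6.2 and 6.3 that GEE comparisons use a small-sample-corrected robust variance (for example n/(n-1) scaling or Mancl-DeRouen) and a t reference on n-1 degrees of freedom, where n is the number of women. Both parts are needed. Report t statistics in place of Z scores.

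For pain, an alternative is to make the permutation test that SAP 6.3 already names the main test, applied within women, and to keep the GEE for estimates.

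The cost is one sentence in each section and a software setting. At n = 24 the intervals for a mean difference become about 8% wider (2.069/1.919 = 1.078). ISR tests become more conservative, especially at low rates: from 4.1% to 2.7% at a 20% rate, and from 1.1% to 0.6% at 10%. Skewed low pain scores may still run slightly above 5% under n/(n-1) scaling; the permutation option avoids relying on that approximation.
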